**Table 2 Target Lesion Visit Responses**

Visit Responses	Description
Complete response (CR)	Disappearance of all TLs since baseline. Any pathological lymph nodes selected as TLs must have a reduction in short axis to <10 mm.
Partial response (PR)	At least a 30% decrease in the sum of the diameters of TL, taking as reference the baseline sum of diameters as long as criteria for PD are not met.
Stable disease (SD)	Neither sufficient shrinkage to qualify for PR nor sufficient increase to qualify for PD
Progression of disease (PD)	A $\geq 20\%$ increase in the sum of diameters of TLs and an absolute increase of $\geq 5\text{mm}$ , taking as reference the smallest sum of diameters since treatment started including the baseline sum of diameters.
Not evaluable (NE)	Only relevant in certain situations (ie, if any of the TLs were not assessed or not evaluable or had a lesion intervention at this visit; and scaling up could not be performed for lesions with interventions). Note: If the sum of diameters meets the progressive disease criteria, progressive disease overrides not evaluable as a TL response.
Not applicable (NA)	No TLs are recorded at baseline.

CR: Complete response; NA: Not applicable; NE: Not evaluable; PD: Progressive disease; PR: Partial response; SD: Stable Disease; TL: target lesion

### **Rounding of Target Lesion Data**

For calculation of PD and PR for TLs percentage changes from baseline and previous minimum should be rounded to 1 decimal place (dp) before assigning a target lesion response. For example, 19.95% should be rounded to 20.0% but 19.94% should be rounded to 19.9%

### **Missing TL Data**

For a visit to be evaluable then all target lesion measurements should be recorded. However, a visit response of PD should still be assigned if any of the following occurred

- A new lesion is recorded
- A NTL visit response of PD is recorded
- The sum of TLs is sufficiently increased to result in a 20% increase, and an absolute increase of  $\geq 5\text{mm}$ , from nadir even assuming the non-recorded TLs have disappeared

Note: the nadir can only be taken from assessments where all the TLs had a LD recorded.

If there is at least one TL measurement missing and a visit response of PD cannot be assigned, the visit response is NE.

If all TL measurements are missing, then the TL visit response is NE. Overall visit response will also be NE, unless there is a progression of non-TLs or new lesions, in which case the

response will be PD.

### **Lymph Nodes**

For lymph nodes, if the size reduces to < 10mm then these are considered non-pathological. However, a size will still be given, and this size should still be used to determine the TL visit response as normal. In the special case where all lymph nodes are < 10mm and all other TLs are 0mm then although the sum may be >0mm the calculation of TL response should be over-written as a CR.

### **Target Lesion Visit Responses Subsequent to Complete Response**

A CR response can only be followed by CR, PD or NE. If a CR has occurred, then the following rules at the subsequent visits must be applied:

- Step 1: If all lesions meet the CR criteria (ie, 0mm or < 10mm for lymph nodes) then response will be set to CR irrespective of whether the criteria for PD of TL is also met ie, if a lymph node LD increases by 20% but remains < 10mm.
- Step 2: If some lesion measurements are missing but all other lesions meet the CR criteria (ie, 0mm or < 10mm for lymph nodes) then response will be set to NE irrespective of whether when referencing the sum of TL diameters, the criteria for PD is also met.
- Step 3: If not all lesions meet the CR criteria and the sum of lesions meets the criteria for PD then response will be set to PD
- Step 4: If after steps 1 – 3 a response can still not be determined the response will be set to remain as CR

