- For TL measurable in 2 or 3 dimensions, always report the longest diameter. For pathological lymph nodes measurable in 2 or 3 dimensions, always report the short axis diameter.

- If the CT/MRI slice thickness used is > 5 mm, the minimum size of measurable disease at baseline should be twice the slice thickness of the baseline scan.
- If a lesion has completely disappeared, the diameter should be recorded as 0 mm. If a lesion appears in the same location on a subsequent scan, it will be recorded as a New Lesion.
- If a TL splits into 2 or more parts, then record the sum of the diameters of those parts.
- If 2 or more TLs merge then the sum of the diameters of the combined lesion should be recorded for one of the lesions and 0 mm recorded for the other lesion(s).
- If a TL is believed to be present and is faintly seen but too small to measure, a default value of 5 mm should be assigned. If an accurate measure can be given, this should be recorded, even if it is below 5 mm.
- If a TL cannot be measured accurately due to it being too large, provide an estimate of the size of the lesion.
- When a TL has had any intervention eg, definitive radiotherapy, embolization, surgery, etc during the study, the size of the TL should still be provided where possible and the intervention recorded in the RECIST case report form. If a TL has been completely removed (surgery), the longest diameter should be recorded as 0 mm.

Evaluation of target lesions

This section provides the definitions of the criteria used to determine objective tumor visit response for TL (see [Table 15](#)).

Table 15 **Evaluation of target lesions**

Complete response (CR)	Disappearance of all TLs since baseline. Any pathological lymph nodes selected as TLs must have a reduction in short axis diameter to < 10 mm.
Partial response (PR)	At least a 30% decrease in the sum of the diameters of TL, taking as reference the baseline sum of diameters.
Stable disease (SD)	Neither sufficient decrease in sum of diameters to qualify for PR nor sufficient increase to qualify for PD.
Progression of disease (PD)	At least a 20% increase in the sum of diameters of TLs, taking as reference the smallest previous sum of diameters (nadir) – this includes the baseline sum if that is the smallest on-study. In addition to the relative increase of 20%, the sum must also demonstrate an absolute increase of at least 5 mm from nadir.

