### **3.3.3 Objective Response Rate**

The ORR is defined for the SAF as follows:

- The ORR is the proportion (%) of patients with an overall response of CR or PR (confirmed by a follow-up scan at least 4 weeks after showing CR or PR).

A confirmed response of CR/PR means that a response of CR/PR is recorded at one visit and confirmed by repeat imaging, preferably at the next regularly scheduled imaging visit, and not less than four weeks after the visit when the response was first observed, with no evidence of progression between the initial and CR/PR confirmation visit. Both visits contributing to the confirmed response must be prior to any subsequent anti-cancer therapy for the patient to be

considered as a responder.

Data obtained up until progression, or the last evaluable assessment in the absence of progression, will be included in the assessment of the ORR. Responses that occur after the start of subsequent anti-cancer therapy must be excluded from the derivation of ORR (ie, only responses that occur prior to receiving subsequent therapy will be included in the numerator).

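### After a target-lesion CR, SAP Step 4 labels a visit CR when a target node has regrown to 10 mm or more without PD, and that visit can confirm the response

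*SAP*

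**What the plan says.** SAP Table 2 defines target-lesion CR with the condition "Any pathological lymph nodes selected as TLs must have a reduction in short axis to <10 mm", and the Lymph Nodes paragraph uses the same limit: "if the size reduces to < 10mm then these are considered non-pathological". For visits after a CR, SAP section 3.1.1.1 opens with "A CR response can only be followed by CR, PD or NE" and then sets out four steps:

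- Step 1: every lesion still meets CR, so the visit is CR.
- Step 2: a measurement is missing and every measured lesion meets CR, so the visit is NE.
- Step 3: a lesion fails CR and the sum meets PD, so the visit is PD.
- Step 4: if "a response can still not be determined the response will be set to remain as CR".

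The general rule under Missing TL Data is "If there is at least one TL measurement missing and a visit response of PD cannot be assigned, the visit response is NE".

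SAP section 3.3.3 treats a response as confirmed when "a response of CR/PR is recorded at one visit and confirmed by repeat imaging", at least four weeks later and without progression in between. Section 3.3.4 requires confirmation for a best response of CR or PR, and section 3.3.5 defines DoR only for confirmed responders.

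**The concern.** Steps 1 to 3 use up every visit at which all measured lesions still meet CR, and every visit that meets PD. What reaches Step 4 is therefore a visit with at least one measured lesion that fails the CR definition. Labelling it CR has two consequences.

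First, when another target lesion is unmeasured, two SAP rules give different answers for the same visit (NE and CR). Two programmers could each code it correctly and disagree.

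Second, section 3.3.3 does not distinguish a CR that meets Table 2 from one carried by Step 4. A single-visit CR can become a confirmed CR on a scan that is not itself a CR. That enters the best-response table and, for some patients, ORR and the set of patients for whom DoR is defined.

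**Working it through.** This is a classification rule and the plan states no figure to reproduce, so the check is to run lesion sizes through the rules. The sizes are illustrations; the documents give no frequencies.

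**Inputs.** CR for a node: below 10 mm (SAP Table 2). PD: a rise of at least 20% and at least 5 mm from nadir (Table 2). A missing lesion counts as zero in the PD test (Missing TL Data). PR: at least 30% below the baseline sum (Table 2). Smallest node eligible as a target lesion: 15 mm short axis (section 3.1.1.1). Treated patients: about 102, of whom 59 are in the standard and 43 in the palliative cohort (SAP section 1.3).

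**Width of the band, one node, all measured.** With nadirs of 5 to 9 mm, 20% is at most 1.8 mm, so the 5 mm condition decides. PD starts at nadir + 5 mm. In steps of 0.1 mm, Step 4 gives CR at:

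- nadir 9 mm: 10.0 to 13.9 mm (PD at 14);
- nadir 8 mm: 10.0 to 12.9 mm;
- nadir 7 mm: 10.0 to 11.9 mm;
- nadir 5 mm: no such range, because PD starts at 10 mm.

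**Worked visits (sizes in mm).**

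| Target lesions | SAP post-CR steps | Table 2 or Missing TL Data |
|---|---|---|
| Node 15 → 9 → 13 | CR (Step 4): +4 mm, 4/9 = +44% | SD: (15−13)/15 = 13.3% below baseline |
| Node 20 → 9 → 12 | CR (Step 4): +3 mm | PR: 8/20 = 40% below |
| Two nodes 16+16 → 9+9 → 11+11 | CR (Step 4): +4 mm, 4/18 = +22% | PR: 10/32 = 31.25% below |
| Node at 9, another lesion missing | NE (Step 2) | NE |
| Node 8 → 12, another lesion missing | CR (Step 4): +4 mm | NE |
| Nodes 9+9 → 22.9, other node missing | CR (Step 4): 22.9−18 = +4.9 mm | NE |
| Nodes 9+9 → 23, other node missing | PD (Step 3): +5 mm, 5/18 = +28% | PD |

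Rows four and five show the reversal: with one lesion unmeasured, a node still below 10 mm gives NE, while a node regrown to 12 mm gives CR. Row six shows how far it extends. The missing node counts as zero against a nadir of 18 mm, so the measured node can more than double and the visit stays CR.

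**Route to the endpoints.** SAP Table 4 carries the target-lesion CR into the overall visit response (CR if non-target lesions are CR or not applicable). In the first row, a CR at Week 8 and a Step 4 CR at Week 16 are eight weeks apart with no progression, so section 3.3.3 makes it a confirmed CR. In the second row the last scan would count as PR under Table 2. The patient would be a responder either way, and only the CR/PR split changes.

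**Size per patient where ORR does change.** 1/102 = 1.0 point overall, 1/59 = 1.7 points in the standard cohort, 1/43 = 2.3 points in the palliative cohort.

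**The case against.** **The SAP deliberately excludes PR and SD after a CR.** This stands. Reading Table 2 alone, one might infer that every Step 4 visit is mislabelled and should be SD, "Neither sufficient decrease in sum of diameters to qualify for PR nor sufficient increase to qualify for PD" in the words of Protocol Table 15. The specific post-CR rule displaces the general table, so carrying the label when all lesions are measured is a convention, not an error. It does not settle whether a carried label should count as confirmation, and NE is also on the permitted list.

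**A missing lesion alone does not produce CR.** A reader might infer from Step 4 that any unmeasured lesion is passed as CR. Step 2 sends that visit to NE. The conflict needs a missing lesion together with a measured one that fails CR without PD.

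**The rule does not always favour the drug.** For response it can only help. For PFS, counting an incomplete scan as evaluable can move a censoring date later, but it can also break a run of missed visits and so keep a later progression as an event (SAP section 3.3.1). DoR ends at the PFS date whatever the label, and adding a patient whose node is regrowing may shorten it.

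**The reach is narrow.** Protocol Appendix F records a lesion that vanished and reappears as a new lesion, hence PD. That confines the gap mainly to nodes, of which at most two can be target lesions. With a baseline node of 20 mm or more and a nadir of 9 mm, the whole single-node band is PR, so ORR does not move. A later scan may also confirm the response properly. SAP section 4.4.3 reports single-visit responses alongside confirmed ones.

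**No rate can be given from the documents.** If measurement error is assumed normal with an SD of 1 to 2 mm, a node truly at 9 mm reads 10 mm or more in 16% to 31% of scans, and one truly at 7 mm in 0.1% to 6.7%. The answer depends on the assumed size and error. A node truly at 9 mm is still a CR, so these are not rates of false CR.

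**Conclusion.** The point holds in a limited form. Where a node has regrown to 10 mm or more without PD and another target lesion is unmeasured, Step 4 contradicts the Missing TL Data rule and ranks a worse scan above a better one. Where all lesions are measured, the carried CR is a stated convention, but the SAP lets a scan that fails its own CR definition confirm a CR.

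The effect is on the confirmed CR count within best response. ORR and entry into DoR are affected only if no other CR or PR visit confirms the response, at about 1.0 point of overall ORR per patient. The documents do not support a general claim of inflated ORR, or a fixed direction for PFS or DoR. The number of patients is unknown and probably small. The endpoints concerned are secondary and descriptive, and the primary endpoint of Grade 3 and 4 possibly related adverse events is unaffected. The conclusion rests on a literal reading of Steps 1 to 4, with missing lesions counted as zero in the PD test.

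**What to change.** Reword Step 4 of SAP section 3.1.1.1 along these lines: *If any target-lesion measurement is missing and PD is not met, set NE, as under Missing TL Data. If all target lesions are measured, CR is carried for the visit, but that visit cannot serve as confirmation of CR; it may confirm a response as PR only if the sum is at least 30% below baseline.* Add a cross-reference in section 3.3.3.

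This keeps the rule that only CR, PD or NE may follow a CR, and leaves the results of Steps 1 to 3 unchanged. The cost is a short SAP edit and a few lines of derivation code. The confirmed CR count or ORR may be lower by an occasional patient.

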### **Target Lesion Too Big to Measure**

If a target lesion becomes too big to measure this should be indicated in the database and a size ('x') above which it cannot be accurately measured should be recorded. If using a value of x in the calculation of target lesion response would not give an overall visit response of PD, then this will be flagged and reviewed by the study team. It is expected that a visit response of PD will remain in the vast majority of cases.

### **Target Lesion Too Small to Measure**

If a TL becomes too small to measure, then this will be indicated as such on the case report form and a value of 5mm will be entered into the database and used in TL calculations. However, a smaller value may be used if the radiologist has not indicated 'too small to measure' on the case report form and has entered a smaller value that can be reliably measured. If a TL response of PD results, then this will be reviewed by the study team.

### **Irradiated Lesions/Lesion Intervention**

A previously irradiated lesion may be selected as a TL, provided that it fulfils the criteria for reproducible measurability and is the only lesion available.

Any TL (including lymph nodes), which has had intervention in addition to study treatment during the study (eg, irradiation / palliative surgery / embolization), should be handled in the following way and once a lesion has had intervention then it should be treated as having

intervention for the remainder of the study noting that an intervention will most likely shrink the size of tumors:

- Step 1: the diameters of the TLs (including the lesions that have had intervention) will be summed and the calculation will be performed in the usual manner. If the visit response is PD this will remain as a valid response category.
- Step 2: If there was no evidence of progression after step 1, treat the lesion diameter (for those lesions with intervention) as missing and if  $\leq 1/3$  of the TLs have missing measurements then scale up as described in the ‘Scaling’ section below. If the scaling results in a visit response of PD then the patient would be assigned a TL response of PD.
- Step 3: If, after both steps, PD has not been assigned, then, if appropriate (ie, if  $\leq 1/3$  of the TLs have missing measurements), the scaled sum of diameters calculated in step 2 should be used, and PR or SD then assigned as the visit response. Patients with intervention are evaluable for CR as long as all non-intervened lesions are 0 (or <10mm for lymph nodes) and the lesions that have been subject to intervention have a value of 0 (or <10mm for lymph nodes) recorded. If scaling up is not appropriate due to too few non-missing measurements, then the visit response will be set as NE.

At subsequent visits the above steps will be repeated to determine the TL and overall visit response. When calculating the previous minimum, lesions with intervention should be treated as missing and scaled up (as per step 2 above).

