6.4 Concomitant therapy

The Investigator must be informed as soon as possible about any medication taken from the time of screening until the end of the clinical treatment phase of the study including the follow-up period following the last dose of study drug.

Any medication or vaccine including over-the-counter or prescription medicines, vitamins, and/or herbal supplements that the patient is receiving at the time of enrollment or receives during the study must be recorded along with:

- Reason for use
- Dates of administration including start and end dates
- Dosage information including dose, unit, and frequency

Patients must be instructed not to take any medications, including over-the-counter products, without first consulting with the Investigator.

Restricted, prohibited, and permitted concomitant medications are described in [Table 6](#) and [Table 7](#). Refer also to the Dosing Modification and Toxicity Management Guidelines (see Section [8.4.5.1](#)).

Table 6 Prohibited concomitant medications

Prohibited medication/class of drug:	Usage:
Any investigational anticancer therapy other than those under investigation in this study	Should not be given concomitantly while the patient is on-study treatment.
mAbs against CTLA-4, PD-1, or PD-L1 other than those under investigation in this study	Should not be given concomitantly while the patient is on-study treatment.
Any concurrent chemotherapy, radiotherapy, immunotherapy, or biologic or hormonal therapy for cancer treatment other than those under investigation in this study	Should not be given concomitantly while the patient is on-study treatment. (Concurrent use of hormones for noncancer-related conditions [eg, insulin for diabetes and hormone replacement therapy] is acceptable. Local treatment of isolated lesions, excluding TLs, for palliative intent is acceptable [eg, by local surgery or radiotherapy]).
Live attenuated vaccines	Should not be given through 30 days after the last dose of durvalumab.

Prohibited medication/class of drug:	Usage:

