Immunosuppressive medications including, but not limited to, systemic corticosteroids at doses exceeding 10 mg/day of prednisone or equivalent, methotrexate, azathioprine, and tumor necrosis factor- α blockers	
 • Should not be given concomitantly, or used for premedication prior to the I-O infusions 
The following are allowed exceptions:
 
 • Use of immunosuppressive medications for the management of durvalumab-related AEs • Use in patients with contrast allergies 
In addition, use of inhaled, topical, and intranasal corticosteroids is permitted.
 
A temporary period of steroids will be allowed if clinically indicated and considered to be essential for the management of nonimmunotherapy related events experienced by the patient (eg, chronic obstructive pulmonary disease, radiation, nausea, etc).

EGFR TKIs	
 • Should not be given concomitantly • Should be used with caution in the 90 days post-last dose of durvalumab 
Increased incidences of pneumonitis (with third generation EGFR TKIs) and increased incidence of transaminase increases (with first generation EGFR TKIs) have been reported when durvalumab has been given concomitantly.

Herbal and natural remedies which may have immune-modulating effects	Should not be given concomitantly unless agreed by the Sponsor.

AE = adverse event; CTLA-4 = cytotoxic T-lymphocyte-associated antigen-4; EGFR = epidermal growth factor receptor; mAB = monoclonal antibody; PD-1 = programmed cell death receptor ; PD-L1 = programmed cell death ligand 1; TKI = tyrosine kinase inhibitor; TL = target lesion.

Table 7 Supportive medications

Supportive medication/class of drug:	Usage:
Concomitant medications or treatments (eg, acetaminophen or diphenhydramine) deemed necessary to provide adequate prophylactic or supportive care, except for those medications identified as “prohibited,” as listed above	To be administered as prescribed by the Investigator
Best supportive care (including antibiotics, nutritional support, correction of metabolic disorders, optimal symptom control, and pain management [including palliative radiotherapy to NTL, etc])	Should be used, when necessary, for all patients
Inactivated viruses, such as those in the influenza vaccine	Permitted

NTL = nontarget lesion.

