### **3.1.1 Site Investigator Assessments Using RECIST 1.1**

#### **3.1.1.1 Target Lesions**

Measurable disease is defined as having at least one measurable lesion, not previously irradiated, which is  $\geq 10$  mm in the longest diameter (LD), (except lymph nodes which must have short axis  $\geq 15$  mm) with CT or MRI and which is suitable for accurate repeated measurements.

A maximum of five measurable lesions (with a maximum of two lesions per organ), representative of all lesions involved and suitable for accurate repeated measurement, should be identified as TLs at baseline. It may be the case that, on occasion, the largest lesion does not lend itself to reproducible measurement. In which circumstance the next largest lesion, which can be measured reproducibly, should be selected. If more than one baseline scan is recorded, then measurements from the one that is closest and prior to initiation of durvalumab will be used to define the baseline sum of TLs.

All other measurable lesions not recorded as TL, and all non-measurable lesions (or sites of disease) should be identified as non-target lesions (NTLs) at baseline. Measurements are not required for these lesions, but their status should be followed at subsequent visits.

For patients who do not have measurable disease at entry (ie, no TLs) but have non-measurable disease, evaluation of overall visit responses will be based on the overall NTL assessment and the absence/presence of new lesions (see Section [3.1.1.3](#) for further details). If a patient does not have measurable disease at baseline, then the TL visit response will be not applicable (NA).

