**Table 3 NTL Visit Responses**

Visit Responses	Description
Complete response (CR)	Disappearance of all NTLs since baseline. All lymph nodes must be non-pathological in size (<10 mm short axis).
Non CR/non PD	Persistence of one or more NTLs with no evidence of progression.
Progression (PD)	Unequivocal progression of existing NTLs. Unequivocal progression may be due to an important progression in one lesion only or in several lesions. In all cases the progression MUST be clinically significant for the physician to consider changing (or stopping) therapy.
Not evaluable (NE)	Only relevant when one or some of the NTLs were not assessed and, in the Investigator's opinion, they are not able to provide an evaluable overall NTL assessment at this visit.  Note: for patients without TLs at baseline, this is relevant if any of the NTLs were not assessed at this visit and the progression criteria have not been met.
Not applicable (NA)	Only relevant if there are no NTLs at baseline.

CR: Complete response; NA: Not applicable; NE: Not evaluable; NTL non-target lesion; PD: Progressive disease; PR: Partial response; SD: Stable Disease; TL: target lesion

To achieve 'unequivocal progression' based on NTLs, there must be an overall level of substantial worsening in non-target disease such that, even in the presence of SD or PR in TLs, the overall tumor burden has increased sufficiently to merit a discontinuation of therapy. A modest 'increase' in the size of one or more NTLs is usually not sufficient to qualify for unequivocal progression status.

Details of any new lesions will also be recorded with the date of assessment. The presence of one or more new lesions is assessed as progression.

A lesion identified at a follow up assessment in an anatomical location that was not scanned at baseline is considered a new lesion and will indicate disease progression.

The finding of a new lesion should be unequivocal: ie, not attributable to differences in scanning technique, change in imaging modality or findings thought to represent something other than tumor.

New lesions will be identified via a Yes/No tick box. The absence and presence of new lesions at each visit should be listed alongside the TL and NTL visit responses.

A new lesion indicates progression, so the overall visit response will be PD irrespective of the TL and NTL response.

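### The SAP has no rule for non-target lesions treated locally on study, so in patients with no target lesions or with target-lesion CR their disappearance can be scored as overall CR

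*SAP*

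**What the plan says.** **What is permitted on treatment.** Protocol 6.4, Table 6, prohibits concurrent cancer therapy but makes an exception: "Local treatment of isolated lesions, excluding TLs, for palliative intent is acceptable". Table 7 lists "palliative radiotherapy to NTL" under best supportive care.

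**Where the intervention rule applies.** SAP 3.1.1.1 (Irradiated Lesions/Lesion Intervention) covers "Any TL (including lymph nodes), which has had intervention in addition to study treatment during the study". It sets out three steps: sum as usual, treat the lesion as missing and scale, then assign a response or NE. Protocol Appendix F also addresses intervention only for TLs: "If a TL has been completely removed (surgery), the longest diameter should be recorded as 0 mm".

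**How NTLs are scored.** SAP 3.1.1.2 derives NTL response from the investigator's overall assessment at each visit. Table 3 defines NTL CR as "Disappearance of all NTLs since baseline", with nodes below 10 mm. It reserves NE for NTLs that were not assessed. Neither entry mentions intervention, although SAP Table 2 does so for TLs.

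**Patients without TLs.** They are eligible (protocol 5.1, inclusion criterion 9a). For those with non-measurable disease only, SAP 3.1.1.1 says "evaluation of overall visit responses will be based on the overall NTL assessment and the absence/presence of new lesions".

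**ORR.** SAP 3.3.3 requires confirmation at least 4 weeks later, and "only responses that occur prior to receiving subsequent therapy will be included in the numerator".

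**The concern.** Under the protocol, NTLs are the lesions that may be treated locally while a patient is on durvalumab, and they are the lesions for which the SAP has no intervention rule. An NTL that has been resected or irradiated away can be recorded as disappeared. In some patients that is enough to complete an overall CR.

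ORR, best response and DoR are reported as durvalumab efficacy in a single-arm trial, so no comparator would show that a response came from local treatment. A no-TL patient scored as a confirmed CR enters the ORR numerator and also contributes a DoR.

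**Working it through.** The plan states no figure on this point, so there is none to reproduce. The check reads SAP Table 4 state by state and then sizes the effect.

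**1. Overall visit response under SAP Table 4, with no new lesion**

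| TL response | NTL CR | NTL Non-CR/Non-PD | NTL NE |
|---|---|---|---|
| CR | CR | PR | PR |
| PR | PR | PR | PR |
| SD | SD | SD | SD |
| NE | NE | NE | NE |
| PD | PD | PD | PD |
| NA (no TLs) | CR | SD | NE |

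NTL CR alters the overall response in 2 of the 6 TL states.

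- TL NA: SD becomes CR. A non-responder becomes a responder, so ORR, best response and DoR all change.
- TL CR: PR becomes CR. The patient is a responder either way, so ORR does not change. DoR does not change either, because SAP 3.3.5 starts it at the first CR or PR that is later confirmed.

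**2. Conditions that must all hold for ORR to change**

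- The patient has no TLs.
- All NTLs are recorded as gone, not only the treated one.
- There is no new lesion.
- The response is confirmed at least 4 weeks later.
- No subsequent anti-cancer therapy has started.

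**3. Whether another rule removes such a case**

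- *Subsequent therapy.* Protocol 7.1.1 records subsequent anticancer therapy, including radiation, from the end of study treatment. Permitted on-treatment palliative radiotherapy sits under supportive care. SAP 3.3.3 does not say whether it counts.
- *Confirmation.* A resected lesion is still absent at the confirming scan.
- *Important protocol deviations.* Deviation 3 (SAP 2.2.1) includes a physician review of procedures before database lock. SAP 4.2.2 then lists and summarises deviations but does not remove patients from ORR.

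None of these takes the patient out of the numerator.

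**4. Size per affected no-TL patient**

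The denominators come from SAP 1.3: about 102 treated, 59 standard and 43 palliative. Shift = 1/N.

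- Overall: 1/102 = 0.98 points
- Standard cohort: 1/59 = 1.69 points
- Palliative cohort: 1/43 = 2.33 points

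The documents give neither the number affected nor an expected ORR. Assuming 1 to 3 patients, the overall shift is 1/102 = 1.0 to 3/102 = 2.9 points. If all three were in the palliative cohort, the shift there would be 3/43 = 7.0 points. For scale, take an assumed 20/102 responders, with Clopper-Pearson 95% CIs:

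- 20/102 = 19.6% (12.4 to 28.6)
- 21/102 = 20.6% (13.2 to 29.7)
- 23/102 = 22.5% (14.9 to 31.9)

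The half-width of the first interval is (28.6 − 12.4)/2 = 8.1 points, so a few such patients would move the estimate by less than its own uncertainty.

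**The case against.** **The route is narrow.** Patients have unresectable Stage III disease, distant metastasis ruled out at entry and 40 to 66 Gy already delivered. A metastasis that appears later is a new lesion and therefore PD, not an NTL. This stands, and it is why the number affected is probably small. It is not negligible by construction, because the documents leave open how many patients will have no TLs. SAP 3.1.1.1 defines measurable disease as not previously irradiated and allows an irradiated TL only if no other lesion is available. The notes to SAP 1.1.2 and inclusion criterion 9b are more permissive.

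**Scoring is not automatic.** The investigator makes the overall NTL assessment, and Table 3 permits CR after local treatment without compelling it. This stands. It makes the outcome possible rather than certain, but it is no safeguard when the written criterion is met.

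**The TL rule is not strict either.** Step 3 says "Patients with intervention are evaluable for CR as long as all non-intervened lesions are 0 (or <10mm for lymph nodes") and the treated lesions are recorded at those values too. A treated TL at 0 mm can therefore count toward CR. This stands: copying the TL rule to NTLs would not close the gap, and scaling could not apply because NTLs are not measured.

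**The TL rule is not misplaced.** The Table 6 restriction applies during study treatment, whereas RECIST assessments continue afterwards and all are used (SAP 3.3). The TL rule therefore has a purpose. The missing piece is a rule for NTLs.

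**Conclusion.** The gap is real and affects secondary endpoints. When the disappearance of all NTLs depends on permitted local treatment, the SAP allows overall CR in patients with no TLs (SD to CR, changing ORR, best response and DoR) and in patients with TL CR (PR to CR, changing best response only). With TL PR, SD, NE or PD nothing changes. Each affected no-TL patient with a confirmed response adds 1.0 point to overall ORR, 1.7 in the standard cohort or 2.3 in the palliative cohort. These sizes rest on the approximate planned cohort sizes. How many patients are affected cannot be derived from the documents.

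A reader might infer that any NTL removed by surgery or radiotherapy will be scored as a durvalumab complete response. The documents do not support that. One treated lesion is not enough, the TL state must be NA or CR, the response must be confirmed to enter ORR, and the NTL score is the investigator's assessment. The primary safety endpoint and its precision calculation are unaffected.

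**What to change.** These changes concern scoring and reporting only.

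1. **SAP 3.1.1.2:** state that from the date an NTL receives local treatment it cannot count as disappeared, so NTL response is capped at Non-CR/Non-PD. PD stays assignable. Use this cap rather than NE. With NE, a no-TL patient's visit becomes overall NE, which SAP 3.3.1 does not treat as evaluable. PFS could then be censored early and true events lost. With the cap, the visit is SD and remains evaluable. For TL CR either choice gives PR.
2. **SAP 3.3.3:** state whether on-treatment palliative local therapy counts as subsequent anti-cancer therapy.
3. **SAP 3.1.1.1, Step 3:** acknowledge that a treated TL at 0 mm can contribute to CR. Either align the TL and NTL rules, or report ORR with and without patients whose CR depends on a treated lesion.
4. **Response listing:** flag the patients concerned.

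**Cost.** This needs a short SAP amendment and one programming flag. ORR or the CR rate may be slightly lower. SAP 3.5.2 already records non-drug therapies, but the details it lists do not include lesion identity, and Appendix F asks for intervention to be entered on the RECIST form only for TLs. Linking a procedure to a particular NTL may therefore need manual review.
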